### 1.2 Definition of terms

**Adverse Event:** An Adverse Event (AE) is any untoward medical occurrence in a patient or clinical investigation subject administered a pharmaceutical product at any dose that does not necessarily have to have a causal relationship with this treatment. An AE can, therefore be any unfavourable and unintended sign (including an abnormal laboratory finding, for example), symptom, or disease temporally associated with the use of an investigational product, whether or not considered related

to the investigational product. This definition includes intercurrent illnesses or injuries and exacerbations of pre-existing conditions.

**Concomitant medication:** All prescription medication, being taken by the subjects on entry to the study and all prescription medication given in addition to the study vaccine during 21 days after each vaccination are to be regarded as concomitant medication

**End of Trial:** The End of Trial corresponds to the last visit of the last subject undergoing the trial (LSLV, Last Subject Last Visit).

**Local and Systemic Reactions:** Selected local and systemic AEs are routinely monitored in vaccine clinical trials as indicators of vaccine reactogenicity. It is recognized that each of these events, and particularly those of a systemic nature, may under some circumstances, in any individual subject, have a cause that is unrelated to the study vaccine. However, as a matter of convenience and in accordance with common clinical practice, all such events occurring within 6 days after immunization are herein termed 'local and systemic reactions'.

**Month, Day:** Study months are based upon 30-day cycles. The study day refers to the number of days after enrollment, with the day of first vaccination being designated day 0.

**Serious Adverse Event:** Any experience or reaction that suggests a significant hazard, contraindication, side effect, or precaution. These events include any experience that is fatal or life-threatening, requires or prolongs inpatient hospitalization, is permanently disabling, leads to congenital abnormality, requires intervention to prevent permanent impairment or damage, or is important and significant medical event that, based upon appropriate medical judgment, may jeopardize the subject.

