**The H1N1v vaccines purchased by the Government** The UK Departments of Health have purchased pandemic vaccines from Baxter Healthcare and GlaxoSmithKline. The Baxter vaccine (trade name, Celvapan) is a plain (i.e., non-adjuvanted), whole virus, vero-cell-grown, influenza A (H1N1)v pandemic formulation, containing 7.5µg HA per 0.5mL dose. The GlaxoSmithKline vaccine (trade name, Pandemrix) is an AS03-adjuvanted, split-product, egg-grown, influenza A (H1N1)v formulation, containing 3.75µg HA and oil-in-water AS03 adjuvant composed of squalene, DL- $\alpha$ -tocopherol and polysorbate 80. The expectation is that the initial limited supplies of both vaccines will be prioritised for those deemed to a greatest risk, but eventually everyone will have access to either vaccine. To ensure that protection is provided as rapidly as possible, it is imperative that vaccine is used efficiently.

**Conclusions** The available evidence indicates that whole virus vaccines, and split and subunit vaccines that contain oil-in-water adjuvant, are more immunogenic for avian H5, H7, and H9 HAs, and A/New Jersey/76 (H5N1) and A/USSR/77 (H1N1) than split and surface antigen vaccines without adjuvant. They also offer the potential for broadened antibody responses that could be critical in the event of antigenic drift during the course of the pandemic. Vaccine is likely to be in short supply (vaccine production takes time and is subject to various rate-limiting factors) and demand will be high worldwide. The available antigen will therefore need to be given optimally with consideration being given to the logistics of vaccine administration, immune responses, and the frequency and nature of adverse clinical reactions.

There have been no head-to-head comparisons of avian vaccines manufactured by Baxter Healthcare and GSK. Due to variability of serological assays, there are uncertainties as to whether

one preparation offers advantages over the other in terms of dose sparing in ‘older’ people, and significantly more ‘seroconversions’ in the young.

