- 17 Individuals who, in the opinion of the investigator, have conditions that might complicate interpretation of the study results;
- 18 Subjects with a history of anaphylaxis or serious reactions to vaccines; known hypersensitivity (other than anaphylactic reaction) to influenza viral protein, to any

component of the study vaccines, to products containing mercury and to residues (egg and chicken protein, ovalbumin, formaldehyde, gentamicin sulphate, sodium deoxycholate, and benzonase).

- 19                               Subjects with a history of any neurological symptoms and signs, or anaphylactic shock following administration of any vaccine;
- 20                               Actual or planned receipt of another vaccine, excluding seasonal influenza vaccine, during the period 3 weeks before to 3 weeks after vaccination on Days 0 and 21.

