#### **6.7.4     Prior and concomitant treatment**

During this trial medication prescribed to the subject prior to the start of the study will not be collected. All prescription medication (except minerals and vitamins), including non-study vaccines, being taken by the subjects on entry to the study and all prescription medication given in addition to the study vaccine during this clinical trial are to be regarded as concomitant medication and must be documented on the Concomitant Medications CRF.

In consideration of the overlapping Northern Hemisphere influenza vaccination campaign, the use of seasonal flu vaccines during the period 3 weeks before to 3 weeks after vaccination on Days 0 and 21 is an exclusion criterion.

All subjects may continue therapy for chronic medical conditions provided that they are not listed in section 8 of the British National Formulary (BNF) or include chloroquine, gold or penicillamine or other drugs listed in section 10.1.3 of the BNF to suppress a chronic disease process. Subjects with chronic medical conditions must be maintained on a stable regimen for at least 2 weeks prior to study entry as assessed by the medical history.

Use of other medication including over-the-counter products should be discouraged during the study. Investigational drugs are prohibited during the course of the study.

The following concomitant treatments are discouraged and, if used, might lead to a major protocol violation and result in withdrawal of the subject from the study according to the medical judgment of the lead physician (See exclusion criteria, 6.7.3; and Removal of subjects from therapy or assessments, 6.7.5):

- Systemic steroids,
- Other immunosuppressive agents,
- Blood or plasma derivatives, including immunoglobulin,
- Non-study vaccines (with the exception of post-exposure vaccinations in a medical emergency, e.g., hepatitis, rabies, tetanus) within 2 weeks.

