### **Visit 8: Day 180 ( $\pm 10$ ): Study termination**

The following activities will be carried out on day 180 and recorded in the CRF:

1. Collect 10ml clotted blood for serology. Process blood and store serum.
2. Ensure Completion of all study termination CRFs.

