**9.2.4 Analysis of immunogenicity criteria**

Blood samples for immunogenicity assays will be collected on Days 0 (prevaccination), 7, 14, 21, 28, 35, 42, and 180.

Antibody response will be evaluated by haemagglutination inhibition (HI), neutralization (MN), and possibly single-radial haemolysis (SRH) in all subjects.

HI and/or MN antibody titres need to be assessed rapidly and so will be analysed in three tranches:

- 1st tranche of sera measuring antibodies before and after 1st injection: Days 0, 7, 14, and 21
- 2nd tranche of sera measuring antibodies before and after 2nd injection: Days 21, 28, 35, and 42.
- 3rd tranche of sera measuring persistence of antibodies: Days 0, 42 and 180.

HI and MN assays will be performed at the Health Protection Agency Centre for Infections, Enteric, Respiratory & Neurological Virus Laboratory, London, UK. SRH tests may be done at the National Institute for Biological Standards and Control. Antibody titrations will be done in duplicate. Pre- and post-vaccination samples from each person will be titrated simultaneously, as specified in the CHMP guidance. The titre assigned will be the geometric mean of two independent determinations.

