#### **9.2.5.2 Secondary immunogenicity measures**

The secondary immunogenicity measures are:

- a. To identify whether one or two doses of vaccine are required to satisfy the licensing criteria. We will assess whether either GSK or Baxter vaccine is able to meet all three CPMP criteria 21 days after the first vaccine dose. This will be assessed for each vaccine/age group, and each vaccine type;
- b. To examine the kinetics of the antibody responses to vaccination. This will be measured in terms of the ability of GSK or Baxter vaccine to meet any one, or all three, of the CPMP criteria 7 and 14 days after the first and second doses – for each vaccine/age group, and each vaccine type;
- c. To examine persistence of antibody at 6 months. This will be assessed in terms of the proportion of vaccinees who have inverse HI antibody titres of  $\geq 40$ , SRH areas of  $\geq 25\text{mm}^2$ , and inverse MN antibody titres of  $\geq 40$  and  $\geq 80$ . Antibody persistence will be assessed for each vaccine/age group, and each vaccine type;
- d. To evaluate the breadth of the antibody response to the antigenic variant (if appropriate, i.e., an antigenic drift variant emerges prior to the 2010-2011 influenza season). This will be done using the new antigenic variant as test antigen in HI, MN, and possibly by SRH tests by comparing the above primary immunogenicity measures on days 21 and 42 for each vaccine, by age group, and all age groups combined.

As with the primary immunogenicity outcomes comparisons will be made using parametric or non-parametric tests as appropriate for continuous outcomes, and Pearson's chi-square test or Fisher's exact test where appropriate for categorical outcomes. Further analyses using (generalised) linear models will explore the effect of baseline covariates on the outcomes. For populations (a) and (b), analyses using multiple imputation to allow for missing data will also be undertaken as a sensitivity analysis. No formal adjustment will be made for multiple testing but associated P-values will be interpreted cautiously.

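### Day 180 persistence can be overstated, and a vaccine difference compressed, because titres raised by non-study influenza vaccine or H1N1 infection after Day 42 count as persistence and such events are not reliably recorded

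*Protocol*

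**What the plan says.** Persistence of antibody at 6 months is a secondary objective (Protocol 5.0). Section 9.2.5.2(c) defines the measure: "This will be assessed in terms of the proportion of vaccinees who have inverse HI antibody titres of" 40 or more, with an SRH area of at least 25 mm² and MN titres of at least 40 and 80, for each vaccine and age group. It sets no condition on what happened between the second dose and the sample.

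Other vaccines are restricted as follows:
- Exclusion 20 (6.7.3) bars other vaccines, "excluding seasonal influenza vaccine, during the period 3 weeks before to 3 weeks after vaccination on Days 0 and 21".
- Section 6.7.4 says the opposite for that window: "seasonal flu vaccines during the period 3 weeks before to 3 weeks after vaccination on Days 0 and 21 is an exclusion criterion".
- Section 6.7.4 also discourages non-study vaccines within 2 weeks, without saying of what, and leaves it to medical judgment whether use is a major violation.

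On access outside the trial, the background (4.0) expects that "eventually everyone will have access to either vaccine".

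On recording, 1.2 says that "all prescription medication given in addition to the study vaccine during 21 days after each vaccination are to be regarded as concomitant medication", while 6.7.4 says that "all prescription medication given in addition to the study vaccine during this clinical trial are to be regarded as concomitant medication". Visit 8 (8.1) lists a blood sample and the instruction "Ensure Completion of all study termination CRFs".

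On analysis, 6.7.5 includes in the immunogenicity assessment everyone with pre- and post-immunisation samples at the scheduled times. The per-protocol set (9.2.2(c)) removes major violations, which are to be defined before analysis.

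**The concern.** The persistence figure is meant to show how long the antibody from two study doses lasts. A later influenza vaccine or infection can lift a subject from below the threshold to above it. A subject already above the threshold is unaffected. The error is therefore upward or nil, and it is larger where the study vaccine has waned more. That flatters the weaker vaccine and narrows any real difference.

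The timing makes such exposure plausible. With a start in early September 2009, Day 180 falls around March 2010. By then a seasonal campaign and a national pandemic programme using both study products would have been running. If the events are not recorded, no later analysis plan can separate the affected sera.

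**Working it through.** **Does any rule cover Day 42 to Day 180?** Exclusion 20 ends 3 weeks after the Day 21 dose: 21 + 21 = Day 42. The sample is due 180 − 42 = 138 days later. Exclusion 20 exempts seasonal influenza vaccine and 6.7.4 does not. The two conflict, but neither reaches past Day 42. The 2-week item in 6.7.4 has no reference date, so it cannot be applied to this interval as written.

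**Would the events be recorded?**
- Under 1.2, concomitant medication stops 21 days after each dose. Under 6.7.4 it runs through the trial, but there the mention of non-study vaccines is attached to medication taken at entry.
- The time and events table has medication history at Visit 1 only. The visit lists ask about new medication at the Day 7 and Day 28 diary reviews.
- Visit 8 names no question on vaccination or influenza. Adverse events are monitored to Day 180, and those leading to a consultation are collected throughout (8.6). Some influenza illness would be caught that way, but an uneventful vaccination would not.

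**How large could the effect be?** The protocol states no Day 180 figure, so there is none to reproduce. Let p be the true proportion at or above the threshold, u the share of those below it who had a later vaccine, and c the chance that the vaccine lifts such a subject over it.

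Reported proportion = p + (1 − p) × u × c, so the shift is (1 − p) × u × c.

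*Seasonal vaccine.* Section 4.0 gives the percentage with cross-reactive MN titre of 160 or more before and after seasonal vaccine. From these, c = (after − before) / (1 − before):

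| Age (years) | Before | After | c |
|---|---|---|---|
| 18–40 | 6% | 7% | 0.01/0.94 = 0.011 |
| 18–64 | 9% | 25% | 0.16/0.91 = 0.176 |
| 60 and over | 33% | 43% | 0.10/0.67 = 0.149 |

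With p = 0.50 and u = 0.30 (both assumed), the shift is 0.50 × 0.30 × 0.011 = 0.2 points at the lowest c and 0.50 × 0.30 × 0.176 = 2.6 points at the highest. At lower uptake it tends to zero.

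*Further pandemic vaccine.* The protocol gives no conversion figure. Assuming c = 0.9:
- p = 0.70, u = 0.10: 0.30 × 0.10 × 0.9 = 2.7 points
- p = 0.50, u = 0.10: 0.50 × 0.10 × 0.9 = 4.5 points
- p = 0.50, u = 0.30: 0.50 × 0.30 × 0.9 = 13.5 points

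*Difference between vaccines.* With the same u and c in both arms, the reported gap is the true gap × (1 − u × c). For an assumed true gap of 30 points (50% against 80%):
- u = 0.5, c = 0.18: 30 × 0.91 = 27.3 points
- u = 0.25, c = 0.9: 30 × 0.775 = 23.3 points

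Infection after Day 42 acts through the same formula, but the protocol gives no attack rate to put into it.

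**The case against.** The strongest reply is that this is mostly silence, which an analysis plan may fill. The per-protocol set provides for a violation list fixed before analysis and aimed at deviations that affect the immunogenicity result. Section 6.7.4 names non-study vaccines and requires entry on the concomitant medication form. The content of the termination forms is not shown. All of that stands, and it leaves a partial route to exclusion. It does not settle the matter, because an analysis plan can remove only what was recorded, and the protocol contradicts itself on how long recording runs.

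A second reply is that few subjects who have had two study doses would seek another pandemic vaccine. The access sentence in 4.0 concerns population supply and says that early stock is limited and goes first to those at greatest risk. This also stands, and it is why the larger pandemic-vaccine figures are conditional.

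A third is that the proportion of all vaccinees above a threshold at 6 months is a legitimate descriptive measure, and that dropping sera after a post-baseline event can itself select subjects. That is right, and both figures should be reported.

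Two stronger readings are tempting. A reader might infer that persistence *is* overstated, by 10 points or more. That needs something like 90% conversion applied to any further vaccine. For seasonal vaccine the protocol's own proxy gives only about 1% to 18%. A reader might also infer that unequal uptake could separate two equal vaccines: with p = 0.50 and c = 0.9, uptake of 5% against 25% gives 52.25% against 61.25%. Nothing in the protocol supports such a split. Under 7.4 subjects are kept unaware of which vaccine they had, and sending interim results to the Department of Health (9.2.7) does not by itself tell a subject their allocation.

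**Conclusion.** The point holds in a limited form. As written, the Day 180 measure can be overstated and a difference between vaccines compressed, because later vaccination or infection is neither restricted by any dated rule, nor handled in the endpoint, nor reliably recorded. The direction is upward or nil.

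The size cannot be stated, because uptake and true persistence are not given. Seasonal vaccine alone suggests roughly 0 to 3 points at 50% true persistence and up to 30% uptake. This assumes that MN titres of 160 or more soon after seasonal vaccine, in other people, stand in for HI titres of 40 or more at Day 180, and that uptake is unrelated to titre. A larger effect requires a material share of subjects to take a further pandemic vaccine.

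This affects a secondary objective and leaves the Day 42 primary assessment untouched. It should still be corrected before Visit 8, because later vaccination is hard to recover reliably afterwards.

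**What to change.** 1. Reconcile 1.2 with 6.7.4 on the recording period, so that non-study vaccines are recorded to Day 180. Reconcile exclusion 20 with 6.7.4 on seasonal vaccine. Which clinical rule applies is for the sponsor to decide.
2. Add to Visit 8 a question on any pandemic or seasonal influenza vaccine, and any confirmed or suspected influenza, since Day 42, with date and product.
3. In 9.2.5.2(c), report persistence for all vaccinees and also excluding Day 180 sera taken after such an event. Name in advance which is the main analysis.
4. Flag a fourfold or greater rise from Day 42 to Day 180 as possible unreported vaccination or infection. The third "tranche of sera measuring persistence of antibodies: Days 0, 42 and 180" already supplies both titres (9.2.4). The flag supplements the question but cannot replace it: a titre that falls from 160 to 20 and is boosted back to 160 shows no rise.

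The cost is one form question and some protocol wording, with no new assay. The restricted analysis loses some sera and precision and may select subjects, which is why both figures are reported.

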***Burden of H1N1 disease, hospitalisations and admissions to ITU*** As of August 7, analysis of the distribution by age of 8974 individual case reports of influenza A(H1N1)v infection in 27 EU/EEA countries reveal that the age-distribution of non-hospitalised cases of H1N1 influenza is highest in the 10-19 year age group, followed by 0-9 and 20-29 year age groups. The age-distribution of hospitalised cases is significantly higher in the 20-29 year age group than in the under 20's. Estimates of transmissibility ( $R_0$  1.4-1.6) are significantly higher than observed in seasonal influenza and comparable to previous pandemics. In England, admission rates have been highest in the under 5's, but life-threatening complications requiring admissions to ITU increase with age and presence of 'high-risk' co-morbidity. It is unclear whether the higher prevalence of infection in the under 30's is related primarily to social mixing, cross-reacting antibodies that are more prevalent with increasing age, or both.

Preliminary studies in the United States have shown that cross-reactive microneutralisation (MN) antibody titres of  $\geq 160$  to A/California/2009 H1N1 were detected in 6% of adults aged 18 to 40 years, 9% of adults 18 to 64 years, and 33% of adults aged 60 years and older. After vaccination with seasonal vaccine, 7% of adults aged 18 to 40 years, 25% of adults aged 18 to 64 years, and 43% of adults aged 60 years and older had post-vaccination titres of  $\geq 160$ .

Infection with the current influenza H1 pandemic virus is mostly mild, with no increase in mortality above threshold national statistics the United States, despite widespread infection. The observed age distribution is unusual and different from seasonal influenza, being skewed towards younger age groups, resulting in deaths and ITU admissions in people who are normally affected less frequently.

Currently it is difficult to be certain about the impact of novel H1N1 infection on hospitalisation rates. A rate of 11% has been observed in the United States, but this is likely to be an overestimate due to the mild nature of the disease in many cases, and differences in clinical practice. An overall rate for Europe is around 5%-6%, but this too may be an overestimate due to the practice in some countries of admitting patients for isolation to control spread, rather than for severity of illness. In the UK, the observed rate has been around 1-2%.

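### Section 9.2.5.2(c): the MN part of six-month persistence takes no account of Day 0 titre, so antibody present before vaccination may count as persistence in the oldest band

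*Protocol*

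**What the plan says.** Persistence of antibody at six months is a listed secondary objective (Protocol, section 5.0). Section 9.2.5.2(c) fixes how it is measured: "This will be assessed in terms of the proportion of vaccinees who have inverse HI antibody titres of" 40 or more, SRH areas of at least 25 mm², "and inverse MN antibody titres of" at least 40 and at least 80. Results are given by vaccine/age group and by vaccine type. No condition is set on Day 0 titre, on Day 42 response or on a rise from baseline. The closing paragraph of 9.2.5.2 applies tests between groups to these outcomes and leaves baseline covariates to exploratory models.

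Section 4.0 reports that "cross-reactive microneutralisation (MN) antibody titres of" 160 or more to A/California/2009 were found in "6% of adults aged 18 to 40 years, 9% of adults 18 to 64 years, and 33% of adults aged 60 years and older". After seasonal vaccine, 7% of those aged 18 to 40, 25% of those aged 18 to 64 "and 43% of adults aged 60 years and older had post-vaccination titres of" 160 or more.

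The Day 0 sera are there to be used. Section 9.2.4 describes the third "tranche of sera measuring persistence of antibodies: Days 0, 42 and 180".

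**The concern.** A subject at MN 160 or above on Day 0 already meets both MN persistence cut-offs before receiving any study vaccine. The exclusion criteria in section 6.7.3 remove confirmed H1N1 infection, recent antiviral use for influenza-like illness and affected household contacts. They do not remove people with cross-reacting antibody. Such a subject would count as persisting at Day 180 whatever the vaccine did, provided the titre did not fall.

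Two things are at stake, mainly in the 65-and-over band. The reported MN persistence could be well above zero for a vaccine whose response had fully waned. The contrast between the two vaccines would also be diluted, because a share of each group would score the same regardless of allocation.

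**Working it through.** The protocol gives no design figure for persistence, so there is nothing to reproduce for the endpoint itself. The group size checks: 60 × (1 − 0.17) = 49.8, or about 50 evaluable (section 9.2.1).

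**Inputs**
- b, the share at or above the MN cut-off at Day 0: 0.33 (section 4.0, age 60+), with 0.43 (after seasonal vaccine) as the upper illustration.
- Group size 60 recruited, about 50 evaluable (section 9.2.1).
- p, the share at or above the cut-off at Day 180 among those below it at Day 0. The protocol gives no value; 0 to 0.6 is assumed for illustration.

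**Step 1: subjects who qualify before dose 1.** MN of at least 160 implies at least 80 and at least 40.
- Age 65+: 0.33 × 60 = 19.8, about 20 per group (0.33 × 50 = 16.5 of the evaluable).
- With 0.43: 0.43 × 60 = 25.8, about 26.
- Younger bands, using the nearest cited figures: 0.06 × 60 = 3.6 and 0.09 × 60 = 5.4.

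The protocol does not give the share at 40 or 80. In the cited population it can only be equal to or higher than the share at 160.

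**Step 2: what the crude endpoint reports.** If baseline titres stay above the cut-off, the observed proportion is b + (1 − b) × p.

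| p | Observed, b = 0.33 | Observed, b = 0.43 |
|---|---|---|
| 0 | 0.330 | 0.430 |
| 0.20 | 0.464 | 0.544 |
| 0.40 | 0.598 | 0.658 |
| 0.60 | 0.732 | 0.772 |

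**Step 3: dilution of a vaccine difference.** The observed difference is (1 − b) × (p₁ − p₂). For p of 0.60 against 0.40:
- b = 0.33: 0.67 × 0.20 = 0.134
- b = 0.43: 0.57 × 0.20 = 0.114

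**Step 4: power in that example** (two-sided 5%, normal approximation for two proportions).
- Crude, 50 per group, 0.732 against 0.598: 0.29.
- Restricted to subjects below the cut-off at Day 0, 50 × 0.67 = 33.5, taken as 34 per group, 0.60 against 0.40: 0.38 (0.37 at 33.5).

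Restriction loses a third of the subjects yet does slightly better. Neither power is adequate.

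**Step 5: what else in the plan refers Day 180 to Day 0** (sections 9.2.5.1 and 9.2.5.2).

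| Measure | HI | SRH | MN |
|---|---|---|---|
| Seroconversion or significant increase from Day 0 to each visit | yes | yes | no |
| Proportion at threshold at each visit, including Day 0 | yes | yes | no |
| Geometric mean at Day 0 and Day 180 | yes | yes | yes |
| Day 180/day 0 geometric mean ratio | no | no | no |

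The ratio list ends at day 42/day 0 for every assay. The individual-level and threshold gaps are confined to MN.

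**The case against.** The strongest reply is that the stated objective is persistence of antibody, not of vaccine-induced antibody, and that the share above a threshold at Day 180 answers this directly. The protocol also does not ignore baseline. It tabulates MN geometric means at Day 0 and Day 180, summarises pre-vaccination antibody (section 9.2.3), and names detectable antibody before vaccination as a factor in the exploratory models (section 9.2.5.3). A split by baseline status could be left to the SAP. This partly stands: the crude proportion is a legitimate description and should stay. But the protocol fixes the measure and plans tests on it, and none of these other items supplies an MN proportion at 40 or 80 on Day 0 or an MN rise to Day 180. Exploratory models do not change the reported proportion.

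A reader might infer more than the documents support:
- **That no assay has a baseline reference.** Section 9.2.5.1 gives HI and SRH both a rise from baseline and threshold proportions at each visit.
- **That 33% held before any vaccine.** Section 4.0 contrasts it only with titres after seasonal vaccine; it does not say those adults had never been vaccinated.
- **That 33% is an established floor here.** It is a preliminary US figure for age 60+, while the trial band is 65 and over in England. Section 4.0 itself stresses variability between laboratories.
- **That the vaccine comparison is biased.** Under 1:1 randomisation the expected share is the same in both groups, so the contrast is diluted, not shifted. Under the sequential allocation of section 7.4 B, baseline levels could differ between vaccines, but section 9.2.5.3 already recognises those comparisons as non-randomised.
- **That a false contrast between age bands is planned.** Item (c) reports within vaccine/age groups and vaccine types and specifies no age-band comparison.

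**Conclusion.** The point holds for MN. As fixed in section 9.2.5.2(c), MN persistence cannot separate antibody present at Day 0 from antibody that lasts after vaccination, and no other specified MN table does so at the level of the subject or the cut-off.

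In the 65-and-over band about 20 of 60 per group (about 26 on the post-seasonal figure) could count as persisting with no lasting vaccine effect. In the illustration, a 20-point difference is reported as about 13 points (about 11 on the post-seasonal figure). In the younger bands the cited pre-seasonal figures suggest only about 4 to 5 of 60.

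These sizes rest on three assumptions: that the cited US prevalence transfers to the trial's band and laboratory, that baseline titres do not fall below the cut-offs over six months, and that 60% against 40% is a fair example. The first two determine the size of the effect; the lack of a baseline reference does not depend on them. For HI and SRH the only remaining gap is the missing day 180/day 0 ratio.

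**What to change.** In section 9.2.5.2(c), keep the crude Day 180 proportions as description. For MN, by vaccine/age group and vaccine type:

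1. show the Day 0 proportion at 40 or more and at 80 or more beside the Day 180 proportion;
2. report the Day 180 proportion at or above each cut-off among subjects below that cut-off at Day 0;
3. add the proportion of subjects with at least a fourfold rise from Day 0 to Day 180.

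In section 9.2.5.1, add day 180/day 0 to the list of geometric mean ratios for all assays. For the MN rise, also state the value assigned to titres below the limit of detection; the section gives one only for HI and SRH.

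No new visit, sample or assay is needed, since the third tranche already covers Days 0, 42 and 180. The cost is smaller denominators for item 2, mainly in the 65-and-over band: about 40 of 60 recruited (60 − 19.8 = 40.2), or 33 to 34 of 50 evaluable, if the 33% applies, and fewer if more subjects are already at 40 or 80.
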